6.2.3.4 Trial completion for an individual patient

A patient is considered to have completed the trial in case any of the following applies:

- Completion of planned follow-up period (or follow-up for overall survival if applicable)
- Lost to follow-up

- Withdrawal to be followed-up
- Death

At the earliest of the above criteria, the Patient Completion (PC) information should be entered in the (e)CRF.

7. STATISTICAL METHODS AND DETERMINATION OF SAMPLE SIZE

[figure not shown]
7.1 STATISTICAL DESIGN – MODEL

This is a single-arm prospective Phase II trial.

[figure not shown]
7.2 DETERMINATION OF SAMPLE SIZE

The sample size calculation was based on the primary endpoint, the objective response rate. Historical data with single agent Cetuximab have yielded response rates of 10-15%, as discussed in Section 1.1. We used Software PASS 2012 (Kaysville, UT) **Inequality Tests for One Proportion** module for sample size calculation. The results were shown in the tables and figures below for different historical control rate. A sample size of 33 will allow us to detect an absolute difference of 20% (alternative hypothesis 30% - null hypothesis 10%) in ORR using a two-sided binomial test with 80% power and significance level of 0.05. Should the historical ORR be 15% (null hypothesis), a sample size of 34 will achieve 80% power to detect an absolute difference of 20% in ORR too.

Null hypothesis: ORR=10%

Null hypothesis: ORR=15%

Based on the calculation as above, we plan to enroll 50 patients which provide us 80% power to detect an alternative hypothetical ORR of 24% by rejecting a null hypothesis of 10%. This

sample size will achieve 80% power to detect an absolute difference of 18% if the historical control of ORR is 15% (i.e. 33% vs. 15%).

7.3 PLANNED ANALYSES

All statistical analyses will be performed using the SAS statistical software, version 9.4 (SAS Institute Inc., Cary, NC). Significance level will be set as $p < 0.05$, two-sided. Yale Center for Analytical Sciences will provide statistical support.

Patient demographics and clinical characteristics will be summarized. The primary analysis will use a 2-sided binomial test to compare the ORR with historical control of 10%. 95% confidence interval of ORR will be reported as well. As an exploratory analysis, Logistic regression will be used to identify potential risk factors that are associated with ORR.

The secondary endpoint is progression-free survival and overall survival with 1 year follow-up. We will use Kaplan-Meier survival analysis to estimate the median PFS and OS in the cohort. Additional Cox regression analyses will be carried out to examine the association between demographical or clinical variables and survival outcome.

We expect 10 – 15 HPV + patients will be enrolled. We will compare the demographics and clinical characteristics between HPV + and HPV - subgroup, and then calculate the ORR by HPV status. An exploratory analysis will be conducted to compare the ORR using multivariate logistic regression, and a survival analysis for the secondary endpoint as well.

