5. VARIABLES AND THEIR ASSESSMENT

5.1 TRIAL ENDPOINTS

5.1.1 Primary endpoint(s)

Objective Response Rate (Complete Response + Partial Response), defined by tumor shrinkage (mm), per Response Evaluation Criteria in Solid Tumors (RECIST) v1.1.

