5.4 ASSESSMENT OF EXPLORATORY BIOMARKER(S)

Pre-treatment biopsies or archived tumor tissue (if no other systemic treatment was administered since that biopsy/excision) will be used to establish a baseline presence and quantification of EGFR, phosphorylated EGFR, and HER2 using immune-fluorescent staining and automated image analysis (AQUA, Genoptix®). These levels will then be compared with levels measured on tumor tissue obtained after 4 weeks of treatment with both Afatinib and Cetuximab to determine effects of treatment and again from tumor tissue obtained at the time of disease progression on treatment. Through sequential measurement of these biomarkers we hope to determine the prevalence of over expression in our patient population, whether EGFR,

phosphor-EGFR and HER2 levels change with treatment with dual EGFR inhibitors and correlate with clinical response and whether they can be used in the future as predictive of response to treatment.

Taking a core needle biopsy (CNB) is anticipated to be the most likely methodology employed in acquiring tissue for analysis in this patient group with advanced cancer of the head and neck region. This can usually be performed in a head and neck surgeon's office under local anesthesia. Tissue samples obtained from all participating sites will be transported to Yale Pathology to [name]'s lab for processing and analysis. Instructions for tissue acquisition and handling, and shipping of samples can be found in the study Laboratory Manual.

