Ultrasound, endoscopy and laparoscopy should not be used to measure tumour lesions or evaluate tumour response. However, these techniques can be useful to supplement information from other techniques.

Cytology and histology can be used to differentiate between PR and CR in rare cases (for example, residual lesions in tumour types such as germ cell tumours where known residual benign tumours can remain).

Baseline Documentation of Target and Non-target Lesions

All measurable lesions up to a maximum of two lesions per organ and five lesions in total, representative of all involved organs should be identified as target lesions and will be recorded, measured (longest diameter = LD) and numbered at baseline. Target lesions should be selected on the basis of their size (lesions with the longest diameter) and their suitability for accurate repetitive measurements (either by imaging techniques or clinically). Lymph nodes must be $\geq 15\text{mm}$ in order to be considered as target lesions.

A sum of the longest diameter (LD) for all target lesions will be calculated and reported as the baseline sum LD. The baseline sum LD will be used as reference to further characterise the objective tumour response of the measurable dimension of the disease (see Table 10.4:1).

Table 10.4: 1 Evaluation of target lesions

Complete Response (CR)	Disappearance of all target lesions.
Partial Response (PR)	At least a 30% decrease in the sum of LD of target lesions taking as reference the baseline sum LD.
Progression (PD)	At least a 20% increase in the sum of LD of target lesions taking as reference the smallest sum LD recorded since the treatment started, together with an absolute increase in the sum of LD of at least 5mm. OR The appearance of one or more new lesions.
Stable Disease (SD)	Neither sufficient shrinkage to qualify for PR, taking as reference the baseline SoD, nor sufficient increase to qualify for PD taking as reference the smallest SoD since the treatment started.

All other lesions (or sites of disease) should be identified as non-target lesions and should also be recorded at baseline. Measurements are not required and these lesions should be followed as "present" or "absent" (see Table 10.4:2).

Table 10.4: 2

Evaluation of non-target lesions and new lesions

Complete Response (CR)	Disappearance of all non-target lesions and normalisation of tumour marker level. All lymph nodes must be non-pathological in size (<10 mm short axis)

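### Section 7.3 ties risk factors and HPV status to response only through binary ORR; a rank analysis of tumour-size change could add roughly 7 to 25 points of power if effects on shrinkage are graded

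*Combined protocol and SAP*

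**What the plan says.** - **Risk factors and HPV (7.3).** As an exploratory analysis, "Logistic regression will be used to identify potential risk factors that are associated with ORR". ORR is also compared by HPV status with multivariate logistic regression, with 10 to 15 HPV-positive patients expected. Cox regression of demographic and clinical variables on survival outcome is planned as well, as is a survival analysis by HPV status.
- **Definition of response (5.1.1, 10.4).** ORR is CR plus PR by RECIST 1.1. For target lesions, PR is "At least a 30% decrease in the sum of LD of target lesions taking as reference the baseline sum LD". Overall response also depends on non-target lesions and new lesions, and CR or PR is to be confirmed.
- **What is measured (10.4).** The sum of target-lesion diameters is calculated at baseline as the reference for later change. Patients are reassessed at weeks 8 and 16 and every 8 weeks after that.
- **Markers (2.1, 5.1.2, 5.4, 5.4.2).** Developing predictive biomarkers is a stated aim, and tissue analysis is a secondary endpoint. Section 5.4 asks whether marker levels "correlate with clinical response and whether they can be used in the future as predictive of response to treatment". Section 5.4.2 will analyse outcome by TP53 status and class. Neither section gives a scale for response or outcome, or a model.
- **Missing data (7.4, 10.4).** Analyses are complete-case without imputation. Evaluability for response needs measurable disease at baseline, at least 3 weeks of therapy and a re-evaluation.

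No section plans an analysis of change in the tumour sum, and none states an effect size or power for the predictor analyses.

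**The concern.** At the planned ORR of 24%, 50 × 0.24 = 12 patients are responders and the other 38 share one value, whether their tumours shrank by 25% or grew by 40%. RECIST justifies that cut for the primary comparison with a historical rate. Nothing in the plan requires it for associations within the trial.

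The loss arises even with one predictor and a well-behaved fit, so it is separate from the problem of fitting several predictors to few responders. It matters more with fewer patients, and biopsies are taken only where feasible, so marker analyses may have well under 50. At stake is the chance of seeing a real graded relation between a factor and shrinkage in measurements that the trial already takes.

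**Working it through.** **1. The plan's own figure.** Section 7.2 plans "50 patients which provide us 80% power to detect an alternative hypothetical ORR of 24% by rejecting a null hypothesis of 10" percent. An exact two-sided binomial test with at most 0.025 per tail rejects upward at 10 or more responses of 50. Its actual size is 0.030 and its power at 24% is 79.3%. For 15% against 33%, the cut is 14 or more, the size 0.027 and the power 81.6%. Both agree with the stated 80%. That power belongs to the primary test only.

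**2. Information kept by the cut.** Suppose tumour change is normal and response is a cut at the ORR p. The efficiency of the binary analysis relative to the continuous one, for small effects, is φ(z)² / [p(1 − p)], with z the upper p quantile.

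- p = 0.24: z = 0.706, φ = 0.311, so 0.0966 / 0.1824 = 0.53.
- p = 0.33: z = 0.440, φ = 0.362, so 0.1311 / 0.2211 = 0.59.

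A continuous test with 80% power has a standardised effect of 1.960 + 0.842 = 2.802. The binary test then has power Φ(2.802 × √0.53 − 1.960) = 53% at ORR 24%, and 58% at 33%.

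**3. Simulated power with a graded effect.** From the plan: two-sided 0.05, N = 50, ORR 24% or 33%. Assumed: latent normal shrinkage Y; a marker X with correlation r to Y; response when Y exceeds its (1 − ORR) quantile; the worst 20% of Y tied at the worst rank to represent early failures; 25, 35 or 50 patients. The tests are the point-biserial test on response (close to the univariable logistic score test) and Spearman on the full scale, with 3,000 to 4,000 replicates per cell. At ORR 24%:

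| n | r | Binary | Rank | Gain (points) |
|---|---|---|---|---|
| 50 | 0.3 | 33.5% | 52.2% | 18.7 |
| 50 | 0.4 | 55.7% | 78.2% | 22.5 |
| 50 | 0.5 | 76.6% | 94.6% | 18.0 |
| 35 | 0.3 | 23.8% | 36.9% | 13.1 |
| 35 | 0.4 | 39.4% | 60.9% | 21.5 |
| 35 | 0.5 | 59.3% | 82.1% | 22.8 |
| 25 | 0.3 | 17.9% | 26.1% | 8.2 |
| 25 | 0.4 | 29.0% | 46.0% | 17.0 |
| 25 | 0.5 | 43.6% | 68.4% | 24.8 |

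At ORR 33% the gain over the same grid is about 8 to 20 points. At an ORR of 10%, the null, it is about 15 to 43. With r = 0 and n = 50, both tests reject 5.1% of the time. The standard error of each power is at most √(0.25 / 3,000) = 0.9 points, and repeat runs put the range at 24% to 33% ORR between 7 and 25 points. With 30%, 40% or 50% of patients tied (n = 50, r = 0.4), the gain is still about 21, 21 and 17 points.

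**4. HPV comparison.** Take 13 positive of 50, within the plan's 10 to 15, and an assumed ORR of 40% against 18%. The overall rate is (13 × 0.40 + 37 × 0.18) / 50 = 23.7%. Power is 36.6% by the score test, 30.8% by Fisher and 48.6% by Wilcoxon on the full scale, a gain of 12.0 points over the score test. As a normal shift of 0.5 to 1.0 SD in favour of 10 to 15 HPV-positive patients, the gain is 7 to 22 points.

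**5. The opposite assumption.** Let the marker raise the log-odds of response by 0.8 per SD but be unrelated to size change within responders or within non-responders, with the same 20% tie. Power is then:

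| ORR | n | Binary | Rank |
|---|---|---|---|
| 24% | 50 | 60% | 35% |
| 24% | 35 | 43% | 24% |
| 33% | 50 | 67% | 47% |

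Here the binary analysis wins by 19 to 25 points.

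**The case against.** The strongest objection is step 5: which analysis is more powerful depends on how a factor acts, and the documents give no evidence on that. This stands, and it is why the proposal adds an analysis and replaces none.

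Other points against, and what remains of them:

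- **Marker analyses.** A reader might infer that the marker and TP53 analyses are also run on binary CR plus PR. The documents do not support this: 5.4 speaks of clinical response and 5.4.2 of outcome, both undefined, while logistic regression in 7.3 is tied to risk factors and HPV status. What stands is that the marker outcome and model are unstated.
- **Other routes to predictors.** The Cox and HPV survival analyses do not use the response cut. They address a different outcome and do not recover the shrinkage information, but the search for predictors is not confined to ORR.
- **Exploratory status.** The logistic analyses carry no power target, so no promise is broken. Binary ORR also keeps them on the same endpoint as the primary test.
- **What the sum omits.** Change in target lesions does not reflect new-lesion or non-target progression, and it needs a follow-up scan. If only 40 of 50 patients had a usable sum (assumed) while all 50 had a binary response, a linear against logistic comparison still gains about 4 to 18 points for r = 0.2 to 0.5. The worst-rank rule deals with early failures, but it conflicts with 7.4 and with evaluability in 10.4 unless both are amended.

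**Conclusion.** The point holds as an inexpensive improvement to exploratory analyses; it does not identify an error. Section 7.3 models response for risk factors and HPV status only as a binary outcome, and the tumour sums are collected but not analysed on their own scale. For a factor with a graded effect on shrinkage, the cost is roughly 7 to 25 points of power at ORR 24% to 33%, and more if the ORR is near 10%.

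That range rests on assumed correlations of 0.3 to 0.5, 25 to 50 patients, a 20% share of tied early failures and a normal shrinkage scale. None of these comes from the plan. A reader might take the range as a loss built into the plan, or conclude that the trial will miss its predictors. Neither follows: the plan states no predictor effect size, and under a pure threshold effect the binary analysis does better. The primary binomial test, N = 50 and the Cox models are unaffected.

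**What to change.** Keep ORR and its binomial test as primary, and keep the logistic analyses. Then:

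1. In 7.3, add a prespecified exploratory analysis of best percent change from baseline in the target-lesion sum for the risk factors and HPV status, using Spearman correlation, the Wilcoxon test or proportional-odds regression. Report it beside the logistic result.
2. In 5.4, name the same outcome and method for the markers. State the outcome for TP53 in 5.4.2 too, since it is undefined.
3. Give the worst rank to patients with death, new-lesion progression or non-target progression before a usable post-baseline sum.
4. Add a matching exception to the complete-case rule in 7.4 and to the evaluability rule in 10.4, limited to this analysis.

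The cost is a few sentences in these sections and a little programming, with no new data, visits or patients. The downside is one more exploratory result per factor, read as tumour-size change and not as response odds, together with the worst-rank convention.

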7.4 HANDLING OF MISSING DATA

We will perform complete case analyses in which those with missing data will be excluded from the relevant analyses. We will not impute missing data. Missing data on one item will not preclude a patient's observed data from being used in other analyses. For example, a patient might have missing response data but observed toxicity data. The toxicity data can be used in appropriate analyses.

8. INFORMED CONSENT, DATA PROTECTION, TRIAL RECORDS

The trial will be carried out in compliance with the protocol, the principles laid down in the Declaration of Helsinki, in accordance with the ICH Harmonised Tripartite Guideline for Good Clinical Practice (GCP) and relevant sponsor's Standard Operating Procedures (SOPs). Standard medical care (prophylactic, diagnostic and therapeutic procedures) remains in the responsibility of the treating physician of the patient.

The investigator must inform the sponsor immediately of any urgent safety measures taken to protect the study subjects against any immediate hazard, and also of any serious breaches of the protocol/ICH GCP.

The rights of the investigator and of the sponsor with regard to publication of the results of this trial are described in the investigator contract. As a general rule, no trial results should be published prior to finalization of the Clinical Trial Report.

8.1 STUDY APPROVAL, PATIENT INFORMATION, AND INFORMED CONSENT

8.1.1 Informed consent

Prior to patient participation in the study, written informed consent must be obtained from each patient (or the patient's legally accepted representative) according to ICH GCP and to the regulatory and legal requirements of the participating country. Each signature must be personally dated by each signatory and the informed consent and any additional patient-information form retained by the investigator as part of the study records. A signed copy of the informed consent and any additional patient information must be given to each patient or the patient's legally accepted representative.

The patient must be informed that his/her personal study-related data will be used by the Principal Investigator in accordance with the local data protection law. The level of disclosure must also be explained to the patient.

The patient must be informed that his / her medical records may be examined by authorized monitors or Quality Assurance auditors appointed by the Sponsor or IRB, and by inspectors from regulatory authorities.

8.1.2 Patient registration

The informed consent process must be completed before any study screening procedures may begin. Following consent, patients will have all required screening procedures outlined in Section 6.2.1. The site principal investigator or other approved investigator must document that the patient has met all inclusion criteria and has none of the exclusion criteria.

8.2 DATA QUALITY ASSURANCE

The YCCI Project Manager will distribute all necessary study related materials and regulatory documents with instructions for their completion and submission to YCCI. Upon receipt of all required regulatory documents including the IRB approved protocol and informed consent form and participation in a study initiation meeting, the Project Manager will send a site activation notice to that participating site. Upon receipt of the activation notice patient screening and consent may proceed.

8.2.1 Data monitoring

The study principal investigator and YCCI are responsible for monitoring the performance of all of the participating sites. This will be performed by conducting a study site initiation visit, as well as regularly scheduled monitoring visits and/or remote monitoring throughout the life of the protocol. At the end of the trial, the monitor will then perform a study site close-out visit at all participating sites.

YCCI will utilize their institution's initiation, monitoring and close-out visit reports. Following each site visit, a visit report will be generated containing information on site activities, and a summary of pertinent points and action items together with a copy of the follow-up letter will be sent to each investigative site.

During these monitoring visits, some of the items that will be reviewed are the following:

- Training of the sites
- Site personnel qualifications to participate in the trial
- That study related documents are current
- That regulatory compliance is accomplished
- That each subject has signed the informed consent
- That the current and approved protocol is complied with (including reporting and logging of all protocol deviations)
- That all SAEs and AEs have been reported to the local regulatory and Ethics/IRB Committees, YCCI, NCCN and Boehringer Ingelheim, as appropriate
- That source documentation matches CRFs
- That required procedures for study drug accountability, distribution, and storage are followed.

YCCI will document the required study monitoring activities in a Study Monitoring Plan.

8.2.2 Safety monitoring

The Study Principal Investigator, biostatistician and study team will monitor toxicity and outcome on a continual basis.

The Yale Cancer Center Data and Safety Monitoring Committee (DSMC) will provide the primary oversight of data and safety monitoring. The Yale DSMC will review and monitor compliance, toxicity and deviations from this study. The committee is composed of clinical specialists with experience in oncology and who have no direct relationship with the study. Information that raises any questions about participant safety will be addressed with the Principal Investigator. The DSMC will review this protocol at a minimum of once every six months. Information to be provided to the committee includes: a study narrative by the PI, a summary DSMC report produced by OnCore (which includes participant accrual, response, trial status history, SAEs, Adverse Events, Deviations and survival); audit results, and monitoring reports as applicable. Other information (e.g. scans, laboratory values) will be provided upon request.

If the committee decides that changes should be made to this trial, recommendations will be made in writing to NCCN, Boehringer Ingelheim and Division Medical Director, which, in turn, have the authority to approve or disapprove these recommendations. These changes will be discussed with the Study Principal Investigator before they are implemented. These changes may include early termination of accrual. Other changes might include altering the accrual goals or changing the eligibility criteria for the trial.

8.2.3 Project team meetings

Scheduled meetings will be held and will include the protocol investigators and research staff involved with the conduct of the protocol.

During these meetings the investigators will discuss:

- Safety of protocol participants (adverse events and reporting)
- Validity and integrity of the data (data completeness on case report forms and complete source documentation)
- Enrollment raterelative to expectation of target accrual, (eligible and ineligible\participants)
- Retention of participants, adherence to the protocol and protocol violations
- Protocol amendments

8.2.4 Audit plan

The YCCI Office of Quality Assurance and Training will audit the trial at least annually or as determined by the YCC DSMC. The overall principal investigator, study coordinator and/or data manager may request access to all source documents and other study documentation for on-site or remote monitoring, audit or inspection.

Involvement in this study as a participating investigator implies acceptance of potential audits or inspections, including source data verification, by representatives designated by the Principal Investigator or Yale. The purpose of these audits or inspections is to examine study-related activities and documents to determine whether these activities were conducted and data were recorded, analyzed, and accurately reported in accordance with the protocol, institutional policy, and any applicable regulatory requirements.

